### **PRIMARY OBJECTIVE**

The cellular outcome measures are as follows:

**To determine whether 4 months of Canagliflozin modifies CD34+ cell number, gene expression and function.**

Protocol for obtaining CD34+ cells: We will obtain a total of approximately 95 mL of peripheral blood per visit. Of these 95 mL, 60-70 mL will be used to obtain CD34+ cells from mononuclear cell (MNC) population and 25-35 mL for biochemistry and plasma ELISA assays. No samples will be stored for future research. MNC will be obtained from whole blood similar to protocols described before. MNCs will be put through CD34 magnetic bead column to obtain CD34+ cells (Miltenyi Biotec). Purity of CD34+ cells, post sort, usually is above 90%, to be verified by FACS analysis.

- A. From Mononuclear (MNC) population (pre CD34+ magnetic column sorting): MNC cells (prior to CD34 magnetic bead sorting) will be also used to assay CFU Hill Colony forming unit (Stem Cell Technologies- Cat#05900) media for Colony Forming unit (CFU) Assay. CFU will be counted on 5-7 days post plating (from initial plating).
- B. From CD 34+ cell population (Post Sorting):
  - a. Migration Assay using SDF1Alpha concentrations of 0, 10, 100ng/ml and VEGF-A concentrations of 20 and 50 ng/ml, using 150,000 cells in 300ul serum free cell suspension media per insert.

- b. Gene expression studies. Genes to be assessed on sorted CD34 positive cells:
  - i. Endothelial lineage cell surface markers: CD34, VEGFR2 (KDR), CD31, CD144
  - ii. For Anti-oxidant gene expression: Superoxide dismutase (SOD) 1, 2 and 3, catalase, glutathione- peroxidase.
  - iii. Apoptosis pathway: p53, p21, Bcl2, caspase-3
  - iv. Endothelial Function Assay Gene: endothelial Nitric Oxide Synthase, von-Willebrand's Factor
  - v. Genes associated with progenitor cell chemotaxis: VEGF-A, SDF1 alpha, CXCR4.

## **SECONDARY OBJECTIVE**

**To determine whether use of Canagliflozin alters other cardio-metabolic health indicator parameters such as: arterial stiffness measures, resting metabolic rate, body composition measures, hs-CRP, IL-6, TNF-alpha (inflammatory markers), fasting lipid profile, levels of insulin, glucose appetite controlling hormones and urine levels of microalbumin (Microalbumin/Creatinine ratio)..**

We expect to corroborate our findings of Aim 1 (cellular outcome measures) with traditional markers of endothelial/ vascular function such as serum biochemistry and arterial stiffness.

### **A. Effect of Cana on Serum Biochemistry & Urine:**

- a. Looking at inflammation, apoptosis and anti-oxidant protein levels: Highly selective C-reactive protein (hs-CRP), IL-1, IL-6, TNF-alpha, MCP-1 , fasting glucose, comprehensive metabolic panel, insulin and lipid profile.
- b. Plasma SDF1 alpha (ELISA) and GLP-1 (ELISA) will be estimated to assess endothelial health and factors that may influence CD34+ cell chemotaxis
- c. Estimation of Creatinine Clearance and proteinuria: 24hr urinary protein estimation and creatinine clearance (obtained via micro-albumin/creatinine ratio from a spot urine sample).
  - i. *Optional sub-study to investigate urine exosomes. See page 31.*
- d. The glomerular filtration rate (GFR) will be estimated using the CKD-EPI (Chronic Kidney Disease Epidemiology Collaboration) equation. The CKD-EPI equation, expressed as a single equation, is:  

$$\text{GFR} = 141 \times \min(\text{Scr}/\kappa, 1)^\alpha \times \max(\text{Scr}/\kappa, 1)^{-1.209} \times 0.993^{\text{Age}} \times 1.018$$
 [if female] X 1.159 [if black]; where Scr is serum creatinine (mg/dL),  $\kappa$  is 0.7 for females and 0.9 for males,  $\alpha$  is  $-0.329$  for females and  $-0.411$  for males, min indicates the minimum of Scr/ $\kappa$  or 1, and max indicates the maximum of Scr/ $\kappa$  or 1.

### **B. Effect of Cana on Body Habitus (Determination of body composition and visceral fat) AND Resting Metabolic Rate.**

- a. Height and weight will be measured and the body mass index (BMI=kg•m-2) used as an indicator of relative weight. The body composition scale calculates body fat% and total body water% in addition to BMI.

- b. We also intend to follow Resting Metabolic Rate (RMR): at weeks 0, 8 and 16. Indirect calorimetric measurements of basal metabolic rate will be obtained using machine obtained from Korrs Medical. This is a noninvasive procedure. We plan to measure the oxygen that the body consumes. It will help us calculate a patient's Resting Energy Expenditure (REE), commonly referred to as a Resting Metabolic Rate (RMR). As our protocol is directed to overweight and obese individuals using incretin therapy, it will be beneficial to note if the treatment modifies RMR. Description: The machine ReeVue by KORR directly measures the concentration of oxygen breathed out by each patient. The patient breathes through a simple mouthpiece as all the exhaled air is collected and analyzed. Because there is a direct correlation between oxygen consumed and calories burned (4.813 calories for every milliliter of oxygen consumed), an accurate measurement of oxygen consumption is an effective measurement of calorie consumption. The machine uses a one-way valve in the disposable (MetaBreather) mouthpiece. This draws in fresh room air with each inspiratory breath and eliminates concerns about cross contamination. The disposable mouthpiece is thrown away. It is un-necessary to clean the equipment or the tubings between each patient. This equipment is FDA approved and has been used in physician offices as an oxygen uptake test with associated CPT code #94690^27. Other related trials have shown weight loss but effect on metabolic rate has not been studied.

**C. Effect of Cana on Assays of Arterial Stiffness:**

- a. We will acquire Pulse wave analysis and Vascular Flow using SphygmoCor CP system from ATCOR as a measure of central arterial pressure and arterial stiffness. Again SGLT2 inhibitors have been shown to reduce systolic blood pressure but effect on stiffness has not been looked at, except with Empagliflozin.
- b. We also intend to acquire Pulse wave analysis and Vascular Flow using SphygmoCor CP system from ATCOR to measure central arterial pressure and arterial stiffness. The secondary measures are indirect measures of endothelial inflammation in early type 2 diabetes patients.

**D. Other Measures:**

- a. Urine pregnancy testing for women of child bearing potential.
- b. Creatinine Clearance and proteinuria estimation (obtained via micro-albumin/creatinine ratio from a spot urine sample).

**STUDY MATERIALS**

Janssen, manufacturers of Cana is expected to provide Cana at no cost for this study.

**SAFETY ASSESSMENTS**

Study drug toxicities will be assessed continuously. Adverse events will be evaluated on a continuous basis while the patient is on study and until 30 days after the last dose of study drug. Patients should be followed until all treatment-related adverse events have recovered to baseline or are deemed irreversible by the principal investigator.

## 7 STATISTICAL CONSIDERATIONS

### **STATISTICAL ANALYSIS**

Sandri et al. (2005, Study A, patients with peripheral arterial occlusive disease) found that in the control group, CD34+ cells increased from 372 cells per mL blood at baseline (SD 156) to 402 (SD 183) at 4 weeks. In their exercise training group, the increase was from 458 (SD 252) at baseline to 2977 (SD 852) at 4-weeks. We created a simulated data set with these parameters in order to calculate the percent of CD34+ cell variation that was explained by the group x time interaction. We tested two random effects mixed models, one without and the other with, a group x time interaction (group is treatment vs control; time is pre vs. 4-weeks post). The percent variance explained =  $(V_{no-int} - V_{int})/V_{no-int}$ , where  $V_{no-int}$  is the residual covariance parameter estimate without a group x time interaction term in the model, and  $V_{int}$  is the residual covariance parameter estimate with a group x time interaction term in the model. We found that based on the baseline and 4-week mean and standard deviation of CD34+ cell concentrations reported by Sandri et al. (2005), the interaction explained 84.5% of the variance in CD34+ cell concentration (a very large effect size). The correlation among repeated measures was  $r=.62$ . Using these parameters in G-Power3 (version 3.1.3), with 2 groups measured at 2 time points, in order to achieve power  $>.95$  would require a total sample size of 6 subjects (3 per group) each measured at 2 time points. Assuming 25% subject loss, we would need to start with 4 per group. If the group x time interaction explained only 50% of the variance in CD34+ cell count (still a large effect), we would need total sample size of 8 (4 per group) in order to achieve power  $>.95$ . In order to account for possible 25% drop-out, 6-8 per group should be randomized.

In Sen et al. (2015), in a sample of patients with pre-diabetes ( $n=11$ ), CD34+ cell number increased from 0.8 (SEM 0.1) before exercise, to 1.4 (SEM 0.2) after exercise, a pre-post effect size (Cohen's  $d$ ) of 1.81. In order to detect an effect of this size using a 2-tailed paired t-test, with  $\alpha=.05$ , for power  $>.80$ ,  $>.90$ , and  $>.95$ , the number of subjects required would be 5, 6, or 7, respectively.

However the two quoted studies quoted above are very different from our proposed study on patients' with established endothelial dysfunction entity such as diabetes. It is well known (Werner et al, Ref No. 11) that diabetes can affect CD34+ number and function, therefore in our proposed study, number of CD34+ cell availability may be a limiting factor. Therefore we propose to use double the number suggested by power calculation and use  $8 \times 2 = 16$  patients per group so that CD34+ cell based end-point studies are not compromised.

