	
20. Active wounds or recent surgery within 3 months. 21. Untreated hyper/hypothyroidism
 
Additionally, patients who are active smokers, patients who are pregnant, nursing women, and post-menopausal women who are on estrogen hormone replacement therapy (not including oral contraceptives) will be excluded.
 
Detailed Inclusion / exclusion criteria are listed on pages 12-15 of the protocol.

Criteria for Evaluation: (Efficacy, safety, stopping rules, etc.)
	
Subjects will be phone screened to determine initial eligibility. If the phone-screening indicates possible eligibility, then the subjects will come to an in-person screening visit at week -2, then evaluated for end points at weeks 0, 8 and 16. Follow up phone call will be done 30 days after last dose of study drug to assess for adverse effects.
 
Study participation will be stopped for adverse effects at the discretion of the study investigator. Subjects may stop study participation at any time and for any reason.

Statistics:
	
The total sample size is requested, after accounting for attrition over the 16-week period, is 20 subjects per group or 40 subjects total. Sample size estimates were based on the effects of exercise on CD34+/KDR+ cells as described in the literature. The effect of a single session, as well as extended training, on healthy subjects or those with existing cardiovascular conditions appears to increase the CD34+/KDR+ cells.
 
This is a pilot study; as a result appropriate power calculation is not feasible. We however did conduct power analysis, which provided us with 73% power (see statistics section). A p-value of less than 0.05 will be considered statistically significant.

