### **Study Design Overview:**

We propose a 2-arm randomized, double-masked, placebo-controlled, parallel group, longitudinal study of 16-weeks duration. (See study design below), recruited over 2 years. The 16 week time interval has been previously shown adequate to observe changes in endothelial progenitor stem cells, biochemistry and importantly, PWV changes. Patients will be randomized to 2 groups:

Control, (n=20), metformin, insulin or Combo + Placebo

Treatment, (n=20) metformin, insulin or Combo + Cana 100mg

This proposed study is based on patients with type 2 diabetes, who are on any combination of the following anti-diabetic therapies: metformin (1-2 grams), insulin, GLP-1 agonists, a DPP-IV inhibitor, or sulfonylureas but still remain poorly controlled with HbA1C between 7.0% and 10% (both inclusive), but not overtly out of control (> 10% of HbA1C).

Though our study is over 16 weeks we do not anticipate significant drop in HbA1C in between the two groups in this relatively short time period to act as a confounding factor on CD34+ cell number, function and gene expression.

Subjects will be taking 100 mg of Cana or placebo. Dose titration of metformin, will not be allowed. Dose titration of insulin will be allowed to avoid hypoglycemia while maintaining HbA1C under 10%.

Most clinical studies looking at HbA1C reduction were of a much longer duration of 6 months or above and most DPP-4 inhibitor studies are with animal EPCs where comparison with human CD34+ population is difficult to make. In one study where saxagliptin was used for 12 weeks

in drug-naïve type 2 diabetes patients there was placebo-subtracted HbA1c reduction noted of 0.45-0.63%. It showed mean placebo-subtracted reductions in fasting serum glucose of 20 mg/dL. From our laboratory studies of in vitro human EPC studies we do not think glucose level change of 20 mg/dL is significant enough to account for changes in EPC number, function and gene expression. However we will take the possibility of glycemia change/ reduction in experimental arm into account during statistical analysis of the results between the Canagliflozin and placebo groups.

*Visits with outcome measurements* will be scheduled for the morning while overnight fasting (except water) to reduce diurnal variability, and clinical parameters will be obtained at scheduled office visits as depicted in the study schema and will be measured at each outcome visit as follows:

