### **DATA ANALYSIS**

Digital data files will be stored in a protected limited-access folder on the MFA network. Only the Study Biostatistician and the PI will have direct access to the data once it is on this server. The data file will have random subject identifiers and will have no HIPAA identifiers.

The distributional assumptions of all measures will be examined. Means and standard deviations will be computed for continuous measures and proportions for categorical variables. Graphical representations of the mean group slopes and individual slopes will be generated and inspected.

Study groups will be compared to determine whether any imbalance between the groups on patient characteristics remain after randomization. If imbalance is evident, by inspection, all models will be adjusted for the unbalanced covariates. Change in outcome over time will be examined using a multilevel approach with linear mixed models (LMM). The longitudinal multilevel modeling approach will enable us to examine characteristics of within-person change, as well as between-group differences that may influence change. LMMs handle missing data more efficiently than traditional ANOVA designs. In the linear mixed models, the patient is considered a random effect and the outcome measured at specific time points is nested within patient. Time (week 0, 8, 16) will be modeled as a continuous variable in order to assess linear effects from 0 to 8 to 16 weeks. In order to determine whether there are non-linear time effects (e.g., rapid increase from 0 to 8 weeks followed by little change from 8 to 16 weeks; or initial decrease at 8 weeks followed by increase at 16 weeks, etc.) we will also need to include models in which time is defined as a class variable (with 0 as the reference group). Subsequent analyses will add study group and other patient characteristics as covariates. We are particularly interested in whether there is a significant interaction between study group and time, adjusting for other patient level covariates. A significant interaction would indicate that the slopes in outcome over time differ by study group. If the global test of interaction is significant, subsequent significance testing of the pair wise comparisons of group slopes group will be adjusted for multiple comparisons. The model also includes coefficients for the group-by-time interactions and random effects for patient and time.

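### The paired, one-group calculation behind 5, 6 or 7 subjects does not give its stated power for the planned canagliflozin-versus-placebo comparison

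*Combined protocol and SAP*

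**What the plan says.** The Statistical Analysis text in Section 7 offers two sizing calculations, both from exercise studies.

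- The plan's first calculation uses a study in peripheral arterial occlusive disease that had a control group. It sizes on the group-by-time interaction and ends at 6 to 8 per group to be randomised.
- The second uses a single group of 11 patients with pre-diabetes, whose CD34+ cell number "increased from 0.8 (SEM 0.1) before exercise, to 1.4 (SEM 0.2) after exercise". The plan calls this "a pre-post effect size" with Cohen's d of 1.81 and states that, "using a 2-tailed paired t-test, with $\alpha=.05$ , for power $>.80$ , $>.90$ , and $>.95$ , the number of subjects required would be 5, 6, or 7, respectively".

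The section then continues: "Therefore we propose to use double the number suggested by power calculation". It reaches 16 per group by doubling 8. The Statistics row of the synopsis says that the sample size estimates rest on exercise effects in the literature.

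The design is given under Study Design Overview: "We propose a 2-arm randomized, double-masked, placebo-controlled, parallel group, longitudinal study of 16-weeks duration". The analysis target is given under Data Analysis: "We are particularly interested in whether there is a significant interaction between study group and time, adjusting for other patient level covariates".

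**The concern.** A paired t-test on one group asks whether that group's mean change differs from zero. The trial asks whether the change on canagliflozin differs from the change on placebo. The second question carries the sampling error of two mean changes, and any change on placebo is subtracted from the effect. The paired calculation contains neither.

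A reader of Section 7 could therefore take 5 to 7 subjects, with power above .80, .90 and .95, as evidence that the placebo-controlled test is easily powered. The figures do not show that. What is at stake is the honesty of the stated justification rather than the planned number of patients.

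**Working it through.** **Inputs.** All come from Section 7, Statistical Analysis, unless noted.

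- Source study: n = 11, mean 0.8 (SEM 0.1) before and 1.4 (SEM 0.2) after; d = 1.81.
- Two-sided alpha .05; the synopsis agrees: "A p-value of less than 0.05 will be considered statistically significant".
- Stated requirement: 5, 6 or 7 subjects.
- Expected retention: 16 per group (Introduction).
- Not given: the pre-post correlation r in the pre-diabetes study. The plan reports r = .62 only for the other exercise study.

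**Step 1. Reproduce the plan's figure.** For a paired t-test, power comes from the non-central t with n − 1 degrees of freedom and non-centrality d√n. With d = 1.81:

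| n | Non-centrality | Power |
|---|---|---|
| 5 | 1.81 × √5 = 4.05 | .851 |
| 6 | 1.81 × √6 = 4.43 | .938 |
| 7 | 1.81 × √7 = 4.79 | .976 |

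At n = 4 the power is .678. So 5, 6 and 7 are correct for a paired test at d = 1.81.

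**Step 2. Same d, planned comparison.** With two time points and equal arms, the group-by-time interaction is a two-sample t-test on change. It has 2n − 2 degrees of freedom and non-centrality d√(n/2), with n per arm. Assume zero mean change on placebo and the same SD of change in both arms.

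| n per arm | Non-centrality | Power | Stated for this n |
|---|---|---|---|
| 5 | 1.81 × √2.5 = 2.86 | .708 | >.80 |
| 6 | 1.81 × √3 = 3.14 | .806 | >.90 |
| 7 | 1.81 × √3.5 = 3.39 | .874 | >.95 |

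If 5, 6 and 7 are read as totals over both arms (2+3, 3+3, 3+4), power is .28, .40 and .48. Neither reading meets the stated levels.

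**Step 3. What 1.81 is.** The implied SDs are 0.1 × √11 = 0.332 before and 0.2 × √11 = 0.663 after. The change is 1.4 − 0.8 = 0.6, and 0.6/0.332 = 1.81. The divisor is the baseline SD. Both tests above need the SD of the change:

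SD of change = √(0.332² + 0.663² − 2r × 0.332 × 0.663) = √(0.55 − 0.44r)

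This equals 0.332 only at r = 1.

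**Step 4. Range over r.** The assumptions are those of Step 2, and r is assumed.

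| r | SD of change | d = 0.6/SD | Paired n for >.80/>.90/>.95 | Two-arm n per arm for >.80/>.90/>.95 | Power at 16 per arm |
|---|---|---|---|---|---|
| 0 | 0.742 | 0.81 | 15/19/22 | 25/34/41 | .60 |
| .5 | 0.574 | 1.04 | 10/12/14 | 16/21/25 | .82 |
| .62 | 0.526 | 1.14 | 9/11/13 | 14/18/22 | .88 |
| .8 | 0.445 | 1.35 | 7/8/10 | 10/13/16 | .96 |

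Power of .80 at 16 per arm needs d = 1.024. That is an SD of change of 0.6/1.024 = 0.586, and so r = (0.55 − 0.586²)/0.44 ≈ .47 or higher.

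**The case against.** The strongest reply is that nothing depends on 5, 6 or 7. The 16 per group doubles 8, the top of the 6 to 8 per group from the plan's first calculation, which does use a control group and the interaction. This stands, and it keeps the severity low. A reader might infer from the doubling sentence that the paired result drives the planned number, or that the trial is therefore too small. The documents support neither inference.

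A second reply is that the plan labels the figure openly as pre-post and paired, and that the synopsis lists pre-to-post change in CD34+ cells among its primary measures. This stands in part: the plan does not expressly claim these powers for the placebo comparison. But the calculation appears as sizing support for a two-arm trial, with no statement that it leaves that comparison unsized.

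A third reply is that the weakness is disclosed. Section 7 says that both source studies differ greatly from this one, and the synopsis says that a proper power calculation is not feasible in a pilot. Those caveats concern the population, cell availability and pilot status. Neither mentions the missing comparator.

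It is also tempting to print 6, 8 and 10 per arm, the two-arm numbers at d = 1.81, and to conclude that 40 patients are ample because 16 per arm would then have power .999. That needs 1.81 to be in units of the SD of change, which holds only at r = 1, so the documents do not support it.

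**Conclusion.** The point holds as a mismatch between the test used for sizing and the planned test. It is not an arithmetic slip, since 5, 6 and 7 reproduce for a paired test at d = 1.81. For the between-arm comparison at that same d, those numbers per arm give .71, .81 and .87 in place of more than .80, .90 and .95.

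Once the effect is scaled by the SD of change, this source study implies anything from 10/13/16 per arm (r = .8) to 25/34/41 per arm (r = 0). Power at the 16 per arm expected to be retained runs from .96 down to .60. The source figures therefore neither show that the planned 40 is sufficient nor show that it is too few.

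These results assume zero change on placebo, equal SD of change in the two arms, two time points and a between-arm effect as large as the exercise effect. The three-visit mixed model could differ somewhat. A rise on placebo would lower the power. The control group in the other exercise study rose from 372 to 402, or 30/372 = 8%, but that is a different population and measurement scale, so it is illustrative only. Severity is low.

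**What to change.** In Section 7, Statistical Analysis, state that the pre-post figure from the pre-diabetes study does not size the placebo-controlled test. Then do one of two things:

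- delete the paired calculation; or
- replace it with a two-arm comparison of change, standardised by the SD of change and reported per arm. State that this study's pre-post correlation is not given in the plan, and show the Step 4 range with its assumptions (zero placebo change, equal SD of change). If the sponsor holds the individual data, the observed SD of change can replace the range.

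Do not give 6, 8 and 10 per arm as the requirement, and do not cite this study as showing that 40 patients suffice. Any case with a placebo rise should be labelled illustrative.

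The cost is a few lines of text and a less favourable stated justification. The change restates figures and does not require enrolling more patients.
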